Research Design and Timeline: We will conduct our work using a mixed-methods, counterbalanced AB crossover design, where intervention A is use of the Explorer Mini, and intervention B is use of the modified ride-on car. All participants at all sites will undergo the same research procedures. Participants will receive both powered mobility interventions, and randomization into two groups at each site will occur to determine which intervention participants will receive first (Modified ride-on car: n = 3; Explorer Mini: n = 3). Three research visits will be scheduled during the study. Baseline assessment (T0) will consist of initial device training and safety checkoff, interview, and administration of outcome measures. Intervention phase 1 will take place for 8 weeks, followed by a mid-study assessment (T1) at which time interviews and outcome measures will be repeated and parent perception/satisfaction with device will be assessed. Training and safety checkoff on the second device will occur. No washout period between devices is indicated because both devices provide self-initiated mobility. Intervention phase 2 will take place for 8 weeks, followed by the final study assessments (T2), where devices will be removed from the participants' homes and a final set of interviews and outcome measures will be administered. During each 8-week study phase, the researchers will conduct two virtual check-ins with each family to answer questions and provide support and standard activity suggestions for device use (i.e. open exploration, switch/joystick play, goal-directed driving).

Equipment:

Modified Ride-On Cars. Commercially available, off-the-shelf, battery-operated rideon toy cars will be modified. *Switch activation*. Unmodified, a child uses their foot to press a pedal or their finger to press a small switch located on the steering wheel to activate the ride-on car which is difficult for young children with CP. Modifications of ride-on cars will include installation of an easy-to-press switch that has a large surface area and responds to a light touch for activation. *Seating support*. Common materials, such as PVC pipe, swimming kickboards, and Velcro will be used to build a

customized supportive seating system. Seatbelts are added in all cars, and fivepoint harnesses are available if needed for appropriate postural support. Cars

Figure 1. Child with CP using a modified ride-on car.

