Sample size justification: A power analysis based on preliminary data was used to determine the number of participants (*N*) necessary to satisfy statistical assumptions for the current study. Power was calculated from the results of the total time (minutes) a modified ride-on car was used between two groups: (1) Families who received bi-weekly support via in-person researcher visits (Mean minutes = 1,060; SD = 783.8), and (2) Families who received no support throughout a 3-month intervention period (Mean minutes = 171.4; SD = 206.1). Beta was set at .80 and alpha at .05 to calculate *N* which is standard practice. Analysis indicates that a sample of 6 participants in each group (modified ride-on cars, Explorer Mini) will produce meaningful treatment differences. This power analysis is appropriate given our hypothesis that the Explorer Mini will be used more frequently and more often than a modified ride-on car based on design features. Also, the above power analysis from previous data is based on between-group differences whereas the current study will examine within-group differences of use patterns between devices, resulting in less variability and greater likelihood of observing differences, if differences exist.

95% confidence intervals and mean number of driving sessions, mean duration (minutes) of driving sessions, and summed total duration (minutes) of driving sessions will be summarized by device type. Variable distributions will be examined to (1) identify appropriate response variable distributions, (2) screen for outliers, and (3) characterize patterns of data missingness. If assumptions for parametric statistics are met, we will use parametric statistics to examine within-subject effects. If assumptions for parametric statistics are not met, we will use the non-parametric equivalent of the planned analyses. A 2

(group: 1, 2) x 2 (time: T1, T2) repeated measures MANOVA will be calculated to determine withinsubject changes on the dependent measures of the mean number of driving sessions, mean duration (minutes) of driving sessions, and summed total duration (minutes) of device use. Significant differences will be followed-up with appropriate post-hoc analyses such as the Bonferonni correction to control for the type I error rate and determine where the significant differences exist.

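### The Aim 2 sample-size assurance takes a support versus no-support gap on the ride-on car as its device effect, so power for the device comparison is not established

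*SAP*

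**What the plan says.** The Aim 2 sample size justification in the SAP draws on preliminary data for total minutes of modified ride-on car use in two groups of families: "Families who received bi-weekly support via in-person researcher visits (Mean minutes = 1,060; SD = 783.8") and "Families who received no support throughout a 3-month intervention period (Mean minutes = 171.4; SD = 206.1"). The error rates are given as "Beta was set at .80 and alpha at .05 to calculate" the sample size. The conclusion is: "Analysis indicates that a sample of 6 participants in each group (modified ride-on cars, Explorer Mini) will produce meaningful treatment differences".

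Two reasons are offered for carrying the result over to the device comparison. The first is the hypothesis: "This power analysis is appropriate given our hypothesis that the Explorer Mini will be used more frequently and more often" than the car because of its design features. The second is that this trial compares devices within children whereas the preliminary data compared groups, "resulting in less variability and greater likelihood of observing differences, if differences exist".

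The SAP plans a 2 x 2 repeated measures MANOVA on three measures (mean number of sessions, mean session duration, total duration), with Bonferroni-type follow-up of significant differences. The 95% intervals accompany summaries by device: "summed total duration (minutes) of driving sessions will be summarized by device type".

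Protocol section 5.1 says: "All participants at all sites will undergo the same research procedures". Each child uses each device for 8 weeks, with two virtual check-ins per phase. Section 2.7 gives a maximum of 18 children.

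**The concern.** A power calculation needs the difference that the trial will compare. The one used here is the effect of researcher support on use of a single device. The SAP then names the two groups as the two devices, which in effect assumes that the Explorer Mini will differ from the car by 888.6 minutes. No Explorer Mini use data, expected device difference or within-child correlation is given to support that. Support, which produced the gap, is the same under both devices here.

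Neither of the SAP's reasons fills the hole. The hypothesis gives a direction without a size. The within-child argument bears on variability, not on the difference itself.

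At stake is how Aim 2 will be read. The plan tells readers that the sample suffices to show device differences, but does not establish what it can detect. With no interval planned for the within-child difference, a non-significant result is harder to interpret: it could reflect similar use, or a difference that the trial could not resolve.

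**Working it through.** **Inputs.** From the SAP: means 1,060 and 171.4; SDs 783.8 and 206.1; alpha 0.05; 0.80, read as power; 6 per group; three use measures. From the protocol: at most 18 children, each using both devices. Not in either document: sidedness, a device difference, an Explorer Mini SD, and the within-child correlation (rho).

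**1. The plan's own figure.** Gap = 1,060 − 171.4 = 888.6. Power for two independent means by noncentral t, df = 2n − 2, noncentrality d × √(n/2):

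- Pooled SD = √((783.8² + 206.1²)/2) = 573.07, so d = 888.6/573.07 = 1.551. At n = 6, power is 80.3% one-sided and 67.8% two-sided. Two-sided, 8 per group are needed (82.2%).
- Simple average SD = (783.8 + 206.1)/2 = 494.95, so d = 1.795. At n = 6, two-sided power is 80.0%.

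So 6 per group follows from the inputs under either of two unstated choices: one-sided with the pooled SD, or two-sided with the average SD.

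**2. What the inputs compare.**

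| | Preliminary data | This trial, Aim 2 |
|---|---|---|
| Contrast | In-person support vs none | Explorer Mini vs ride-on car |
| Device | Ride-on car only | Both, in each child |
| Support | Differs between groups | Same for both devices |
| Period | 3 months | 8 weeks per device |

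**3. Power for the device contrast.** Crossover contrast on one measure, two-sided 0.05, N = 18, df = N − 2 = 16. Assume equal SDs on both devices and rho = 0. SD of the within-child difference = SD × √(2(1 − rho)); noncentrality = (difference / that SD) × √18.

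- Full gap, SD 783.8: 888.6/1,108.5 = 0.802; noncentrality 3.40; power 89%.
- Quarter gap (222.15), SD 783.8: 0.200; noncentrality 0.85; power about 12%.
- Quarter gap, SD 573.07: 222.15/810.4 = 0.274; noncentrality 1.16; power 19%.
- Quarter gap, SD 206.1: 222.15/291.5 = 0.762; noncentrality 3.23; power 86%.

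All three SDs come from the SAP's figures. The trial's level of support matches neither preliminary group, so nothing shows which SD applies. A positive rho would raise every one of these powers.

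**4. What the design can detect and estimate, without minutes.** In SDs of the within-child difference; half-width = t(0.975, N − 2)/√N:

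| Completers | 80% power, one measure, alpha 0.05 | 80% power, alpha 0.05/3 | 95% CI half-width |
|---|---|---|---|
| 18 | 0.70 | 0.84 | 0.50 |
| 16 | 0.75 | 0.90 | 0.54 |
| 14 | 0.82 | 0.99 | 0.58 |

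**5. The planned joint test.** For three measures (Hotelling's T², error df 16, N = 18), 80% power needs a multivariate (Mahalanobis) difference of about 0.90. At a multivariate difference of 0.70, power is about 57%. The figures in step 4 are therefore not the power of the planned MANOVA.

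**The case against.** The SAP is open about where its inputs come from and about the between-group versus within-child mismatch. The justification closes on a conditional clause about differences existing. The Aim 1 text calls the proposal a pilot, with few children and no confirmatory claim. If the device difference were as large as the borrowed gap, 18 children in a crossover would have at least 89% power under the least favourable SD and rho used above. Other parts of the SAP also plan to describe differences in use by device type.

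Much of this stands, and it limits the point. Disclosure lets a reader see the mismatch but does not turn a support effect into a device effect. The condition qualifies the variability sentence and leaves the assurance itself unqualified. For Aim 1 the SAP says that it has no prior data for a power calculation; the documents contain none on a device difference either.

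A reader might go further and infer that 6 per group is an arithmetic error. It is not, since two ordinary choices give 80%. A reader might also infer that a null Aim 2 result could not be interpreted at all. That goes too far: such a result is read from the observed data, and by-device intervals are planned. What is missing is the interval for the paired difference. The shorter period is not decisive alone either, because standardised figures do not change if minutes and SD shrink in proportion.

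**Conclusion.** The concern holds in this form: the Aim 2 assurance rests on an unsupported assumption that the devices differ by the size of a support effect, and power for the device comparison is not established. It depends on the device difference, the SD and the within-child correlation. The documents give no estimate of the first or third for this comparison, and two quite different SDs for the second. At a quarter of the gap, with 18 children and rho assumed 0, the choice of SD alone moves power from about 12% to 86%.

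A reader might conclude that the trial is underpowered. The documents do not support that, as the 89% at the full gap shows; the same uncertainty prevents the opposite assurance. These figures rest on equal SDs on both devices, a two-sided univariate crossover contrast and 18 completers, the stated maximum. This should be fixed, but it does not call the design into question.

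**What to change.** 1. Delete the sentence that 6 per group will show treatment differences. State instead that the preliminary data compare supported with unsupported families on the ride-on car over 3 months and do not estimate a device difference.
2. Plan to report the 95% confidence interval for the within-child device difference on each use measure, beside the by-device intervals. Give its expected half-width: about 0.50, 0.54 or 0.58 SD of the within-child difference with 18, 16 or 14 completers.
3. If a detectable difference is stated, label it as a univariate, two-sided 0.05 crossover contrast on one measure: about 0.70, 0.75 or 0.82 SD for 80% power with 18, 16 or 14 completers (0.84, 0.90 or 0.99 with Bonferroni over three measures). Say that this is not the power of the planned three-measure MANOVA, which needs a multivariate difference of about 0.90 with 18 completers. Omit figures in minutes, which would need an assumed correlation and SD.
4. In "Beta was set at .80 and alpha at .05 to calculate", replace Beta with power; a literal beta of 0.80 would mean 20% power.

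The cost is one rewritten paragraph, one more reported interval per use measure, and a less favourable statement about the sample. The number of children, the design and the planned test do not change.
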